#### **4.5.6 Treatment Beyond Disease Progression**

Accumulating evidence indicates a minority of subjects treated with immunotherapy may derive clinical benefit despite initial evidence of PD.

Subjects will be permitted to continue on nivolumab alone or in combination with ipilimumab (Arm A) or chemotherapy (Arm B) for treatment beyond initial RECIST 1.1 defined PD, assessed by the investigator up to a maximum of 24 months from date of first dose as long as they meet the following criteria:

- Investigator-assessed clinical benefit.
- Tolerance of study drug
- Stable performance status
- Treatment beyond progression will not delay an imminent intervention to prevent serious complications of disease progression (eg, CNS metastases)
- Subject provides written informed consent prior to receiving additional nivolumab alone or in combination with ipilimumab (Arm A) or chemotherapy (Arm B). All other elements of the main consent including description of reasonably foreseeable risks or discomforts, or other alternative treatment options will still apply.

A radiographic assessment/scan should be performed within 6 weeks of initial investigator-assessed progression to determine whether there has been a decrease in the tumor size or continued PD. The assessment of clinical benefit should be balanced by clinical judgment as to whether the subject is clinically deteriorating and unlikely to receive any benefit from continued treatment with nivolumab or nivolumab plus ipilimumab or nivolumab plus fluorouracil and cisplatin.

If the investigator feels that the subjects treated with nivolumab or nivolumab plus ipilimumab or nivolumab plus fluorouracil and cisplatin continues to achieve clinical benefit by continuing treatment, the subject should remain on the trial and continue to receive monitoring according to the Time and Events Schedule in [Section 5.1](#).

For the subjects in Arms A or B who continue nivolumab alone or in combination with ipilimumab (Arm A) or chemotherapy (Arm B) beyond progression, further progression is defined as an additional 10% increase in tumor burden with a minimum 5 mm absolute increase from time of initial PD and an appearance of another new lesion. This includes an increase in the sum of diameters of all target lesions and/ or the diameters of new measurable lesions compared to the time of initial PD. Nivolumab alone or in combination with ipilimumab (Arm A) or chemotherapy

(Arm B) treatment should be discontinued permanently upon documentation of further progression.

New lesions are considered measureable at the time of initial progression if the longest diameter is at least 10 mm (except for pathological lymph nodes which must have a short axis of at least 15 mm). Any new lesion considered non-measurable at the time of initial progression may become measureable and therefore included in the tumor burden if the longest diameter increases to at least 10 mm (except for pathological lymph nodes which must have a short axis of at least 15 mm). In situations where the relative increase in total tumor burden by 10% is solely due to inclusion of new lesions which become measurable, these new lesions must demonstrate an absolute increase of at least 5 mm.

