### **3.5 Discontinuation of Subjects following any Treatment with Study Drug**

Subjects MUST discontinue investigational product (and non-investigational product at the discretion of the investigator) for any of the following reasons:

- Subject's request to stop study treatment
- Any clinical AE, laboratory abnormality or intercurrent illness which, in the opinion of the investigator, indicates that continued participation in the study is not in the best interest of the subject
- Termination of the study by BMS
- Loss of ability to freely provide consent through imprisonment or involuntarily incarceration for treatment of either a psychiatric or physical (eg, infectious disease) illness. (Note: Under specific circumstances, a participant who has been imprisoned may be permitted to continue as a participant. Strict conditions apply and BMS approval is required.)
- Criteria listed in [Section 4.5.5](#)
- Disease progression as assessed by RECIST 1.1 criteria, unless the subject meets criteria for treatment beyond progression ([Section 4.5.6](#)).

In the case of pregnancy, the investigator must immediately notify the Sponsor or designee of this event. In most cases, the study drug will be permanently discontinued in an appropriate manner (eg, dose tapering if necessary for subject safety). Please contact the Sponsor or designee within 24 hours of awareness of the pregnancy. If the investigator determines a possible favorable benefit/risk ratio that warrants continuation of study drug, a discussion between the investigator and the Sponsor or designee must occur.

All subjects who discontinue study drug should comply with protocol specified follow-up procedures as outlined in [Section 5](#). The only exception to this requirement is when a subject withdraws consent for all study procedures including post-treatment study follow-up or loses the ability to consent freely (ie, is imprisoned or involuntarily incarcerated for the treatment of either a psychiatric or physical illness).

If study drug is discontinued prior to the subject's completion of the study, the reason for the discontinuation must be documented in the subject's medical records and entered on the appropriate case report form (CRF) page.

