    - Dosing delays  $> 8$  weeks that occur for non-drug-related reasons may be allowed if approved by the BMS Medical Monitor. Prior to re-initiating treatment in a subject with a dosing delay lasting  $> 8$  weeks, the BMS Medical Monitor must be consulted. Tumor assessments should continue as per protocol even if dosing is delayed.
  - Any adverse event, laboratory abnormality, or intercurrent illness which, in the judgment of the Investigator, presents a substantial clinical risk to the subject with continued treatment.

Subjects could be discontinued from any or both of the study drugs on the FP regimen if, in the opinion of the investigator it is inappropriate to continue on the basis of safety or efficacy.

Subjects who discontinue one of the study drugs on the FP regimen may at the investigators discretion continue administration of the other study drugs. For example, if Cisplatin is discontinued, 5FU may be continued at the intended dose and schedule.

For subjects in Arm B, if the investigator is unable to determine whether an adverse event is due to nivolumab or to fluorouracil and cisplatin combination, then all drugs must be discontinued.

The assessments for discontinuation of chemotherapy and/or nivolumab in Arm B should be made separately. It is allowed to continue nivolumab alone when chemotherapy has been discontinued. Chemotherapy doublet or single drug is allowed to continue if nivolumab met its discontinuation criteria.

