## 3 TUMOR RESPONSE EVALUATION

### 3.1 Evaluation of Target Lesions

- Complete Response (CR): **Disappearance of all target lesions**. Any pathological lymph nodes (whether target or nontarget) must have reduction in short axis to < 10 mm.
- Partial Response (PR): At least a **30% decrease in the sum of diameters of target lesions**, taking as reference the baseline sum diameters.
- Progressive Disease (PD): At least a **20% increase in the sum of diameters of target lesions**, taking as reference the **smallest sum on study** (this includes the baseline sum if that is the smallest on study). In addition to the relative increase of 20%, the sum must also demonstrate an **absolute increase of at least 5 mm**. (Note: The appearance of 1 or more new lesions is also considered progression).
- Stable Disease (SD): Neither sufficient shrinkage to qualify for PR nor sufficient increase to qualify for PD, taking as reference the smallest sum on study.

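### Protocol 4.5.6 requires growth and another new lesion for further progression, so tumor growth alone, however large, never triggers the mandatory permanent stop in Arms A and B

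*Protocol*

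**What the plan says.** Protocol 4.5.6 gives the permission: "Subjects will be permitted to continue on nivolumab alone or in combination with ipilimumab (Arm A) or chemotherapy (Arm B) for treatment beyond initial" progression, by RECIST 1.1 and as judged by the investigator, for at most 24 months from first dose. The conditions are clinical benefit in the investigator's judgment, tolerance of study drug, stable performance status, no delay of an imminent intervention against serious complications, and separate written consent. A scan is due within 6 weeks of initial progression "to determine whether there has been a decrease in the tumor size or continued PD".

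The section then defines further progression in these terms: "10% increase in tumor burden with a minimum 5 mm absolute increase from time of initial PD and an appearance of another new lesion". The next sentence says what the increase covers: "an increase in the sum of diameters of all target lesions and/ or the diameters of new measurable lesions", compared with initial progression. The mandatory consequence follows: nivolumab alone or in combination (Arm A with ipilimumab, "Arm B) treatment should be discontinued permanently upon documentation of further progression".

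The closing paragraph of 4.5.6 sets out when new lesions are measurable. It adds that if the 10% is reached only because new lesions have become measurable, those lesions must themselves have grown by at least 5 mm.

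Outside 4.5.6, section 3.5 lists among the mandatory reasons to stop: "Disease progression as assessed by RECIST 1.1 criteria, unless the subject meets criteria for treatment beyond progression".

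**The concern.** Once a subject is being treated past progression, most of what keeps that subject on drug is the investigator's judgment of benefit, in an open-label trial. Further progression is the only stop after that point that rests on tumor size. It should catch the subject whose disease plainly keeps advancing on scans while the judgment of benefit stays favorable.

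As worded, it does not catch continued growth. A subject whose known lesions keep enlarging, with no further lesion appearing, never meets the definition. What is at stake is exposure: nivolumab and ipilimumab in Arm A, nivolumab with or without cisplatin and fluorouracil in Arm B, continued in someone whose tumor is growing without any imaging rule that ends it.

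Two other places make the wording look odd. For first progression, Appendix 5 section 3.1 treats target growth as sufficient and adds that "The appearance of 1 or more new lesions is also considered progression", so each route counts on its own. And the scan within 6 weeks looks for continued progression, yet growth on that scan triggers no mandatory stop. These are weaker signs than the wording inside 4.5.6 itself, as discussed below.

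**Working it through.** The point rests on the wording. The plan states no figure to reproduce, and no sample size, power or alpha enters.

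**1. The definition as a rule.** Let B0 be tumor burden at initial progression and B1 the burden at a later scan.

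- Growth part G: (B1 − B0)/B0 ≥ 10% and B1 − B0 ≥ 5 mm.
- New-lesion part N: another new lesion has appeared.
- Section 4.5.6 as written: further progression = G and N.

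**2. When the growth part is met.** The smallest qualifying burden is B0 + max(0.10 × B0, 5 mm). The documents give no burdens, so the B0 values are assumed.

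| Assumed B0 | max(10%, 5 mm) | G met at | Increase |
|---|---|---|---|
| 30 mm | 5 mm | 35 mm | 5/30 = 16.7% |
| 50 mm | 5 mm | 55 mm | 10% |
| 60 mm | 6 mm | 66 mm | 10% |
| 100 mm | 10 mm | 110 mm | 10% |
| 150 mm | 15 mm | 165 mm | 10% |

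**3. The full rule at an assumed B0 of 100 mm.**

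| Later scan | G | N | As written | New-lesion clause deleted |
|---|---|---|---|---|
| 110 mm, another new lesion | yes | yes | stop | stop |
| 110 mm, no new lesion | yes | no | no mandatory stop | stop |
| 200 mm, no new lesion | yes (+100%) | no | no mandatory stop | stop |
| 100 mm including any measurable new lesion | no | yes | no mandatory stop | no mandatory stop |

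Rows two and three are the gap. No value of B1 closes it, because N does not depend on B1.

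**4. The definition against the rest of 4.5.6.**

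- The sentence on what the increase covers joins target-lesion growth and new measurable lesions by and/or. Under it, target growth alone can supply the whole increase. It says what counts toward G and does not remove N, but it reads as if G were the decision.
- The 5 mm safeguard concerns lesions that were non-measurable at initial progression and later reach measurable size (10 mm, or 15 mm short axis for nodes). A lesion that crosses the threshold adds its whole diameter to the burden although it may have grown little. The safeguard stops that arithmetic from producing a false further progression. It has a clear purpose if G alone decides. If yet another new lesion is always needed as well, it has little left to do.

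Neither sentence makes G sufficient. The definition is not restated elsewhere in the protocol or in the SAP, so the literal conjunction stands.

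**5. What deleting the clause would still capture.** A measurable non-nodal lesion absent at initial progression and first seen at 10 mm adds 10/B0 to the burden. If the other lesions are unchanged, that is at least 10% for B0 up to 100 mm. At an assumed 150 mm it is 10/150 = 6.7%, which is not enough alone. A new non-measurable lesion without growth would remain outside the rule.

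**The case against.** The strongest reply is that stops exist elsewhere and do not need a new lesion. Treatment past progression is an exception that lasts only while its conditions hold, and section 3.5 makes stopping the mandatory default when they fail. A subject who has grown and lost clinical benefit, tolerance or stable performance status must stop, as must one for whom continuing would delay an imminent intervention. Performance status is more than an opinion about benefit: ECOG is scheduled at dosing visits in both arms (Tables 5.1-2 and 5.1-3) on the scale in Appendix 3. Chemotherapy may also be ended if "in the opinion of the investigator it is inappropriate to continue on the basis of safety or efficacy" (section 4.5.5.2). All of this stands. It means the point concerns the imaging backstop and not stopping rules in general. It does not close the gap, because none of these routes has a tumor-size threshold.

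A second reply is that a stricter second threshold is a coherent choice when some subjects benefit despite initial progression. That disposes of the comparison with Appendix 5, which governs first progression. The 6-week scan can likewise be read as informing the judgment of benefit. But a deliberate requirement for a new lesion fits poorly with the and/or sentence and the 5 mm safeguard, and the protocol gives no reason for it. A drafting slip is the likelier explanation.

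A reader might also see a conflict over Arm B chemotherapy, which other sections run until progression while 4.5.6 lets it continue. That is a general rule with a specific exception: section 3.1.2.2 refers to 4.5.6, and section 3.5 recognizes the exception. It is not part of this point.

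**Conclusion.** The wording is wrong as it stands and should be corrected. Growth alone, at any size, does not meet the only tumor-size criterion for permanent discontinuation after initial progression in Arms A and B.

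Its size can be stated only as logic. The documents give no rate of treatment beyond progression, no distribution of tumor burden, and no share of subjects who grow without a new lesion, so the number affected cannot be derived. The millimeter examples use assumed burdens and illustrate the rule; they do not estimate frequency.

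Two stronger readings are tempting and are not supported. The first is that a subject with unchecked growth can never be made to stop: the conditions in 4.5.6, the default in section 3.5 and the 24-month limit all apply. The second is that the efficacy results are biased: primary PFS ends at first progression per BICR or death (Protocol 8.3.1, SAP 4.1.2), so a rule that acts only after investigator-assessed progression does not alter its definition, and no effect on OS can be derived. This is a point about patient safety and exposure. It rests on reading the conjunction literally, which is how a site would have to apply it.

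**What to change.** In Protocol 4.5.6, delete the clause that requires another new lesion. An additional 10% increase of at least 5 mm from initial progression, counting target lesions and/or new measurable lesions as the next sentence already provides, would then mandate permanent discontinuation. The 5 mm safeguard for lesions that become measurable stays as it is.

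The change is one clause in a protocol amendment. It needs no new data and leaves alpha, power and the PFS definition untouched. The cost falls on some Arm A and Arm B subjects with growth but no new lesion, who would stop study drug earlier, including a few who might still benefit. A new non-measurable lesion without growth would remain a matter for the investigator. Replacing the conjunction with an alternative would cover that case too, but would also stop a subject with one small new lesion and no growth; deletion is the more measured change.

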#### **4.5.7 Management Algorithms for Immuno-oncology Agents**

Immuno-oncology (I-O) agents are associated with AEs that can differ in severity and duration than AEs caused by other therapeutic classes. Nivolumab and ipilimumab is considered an I-O agent in this protocol. Early recognition and management of AEs associated with I-O agents may mitigate severe toxicity. Management Algorithms have been developed to assist investigators in assessing and managing the following groups of AEs:

- Gastrointestinal
- Renal
- Pulmonary
- Hepatic
- Endocrinopathy
- Skin
- Neurological

The above algorithms are found in the nivolumab Investigator Brochure and [Appendix 1](#) of this protocol.

#### **4.5.8 Treatment of Nivolumab or Ipilimumab Related Infusion Reactions**

Since nivolumab and ipilimumab contains only human immunoglobulin protein sequences, it is unlikely to be immunogenic and induce infusion or hypersensitivity reactions. However, if such a reaction were to occur, it might manifest with fever, chills, rigors, headache, rash, pruritus, arthralgias, hypotension, hypertension, bronchospasm, or other allergic-like reactions. All Grade 3 or 4 infusion reactions should be reported within 24 hours to the study medical monitor and reported as an SAE if it meets the criteria. Infusion reactions should be graded according to NCI CTCAE version 4 guidelines.

Treatment recommendations are provided below and may be modified based on local treatment standards and guidelines, as appropriate:

For Grade 1 symptoms: (mild reaction; infusion interruption not indicated; intervention not indicated):

- Remain at bedside and monitor subject until recovery from symptoms. The following prophylactic premedications are recommended for future infusions: diphenhydramine 50 mg (or equivalent) and/or acetaminophen/paracetamol 325 to 1000 mg at least 30 minutes before additional nivolumab or ipilimumab administrations.

For Grade 2 symptoms: (moderate reaction required therapy or infusion interruption but responds promptly to symptomatic treatment (eg, antihistamines, non-steroidal anti-inflammatory drugs, narcotics, corticosteroids, bronchodilators, IV fluids); prophylactic medications indicated for ≤ 24 hours):

- Stop the nivolumab or ipilimumab infusion, begin an IV infusion of normal saline, and treat the subject with diphenhydramine 50 mg IV (or equivalent) and/or acetaminophen/paracetamol 325 to 1000 mg; remain at bedside and monitor subject until resolution of symptoms. Corticosteroid and/or bronchodilator therapy may also be administered as appropriate. If the infusion is interrupted, then restart the infusion at 50% of the original infusion rate when symptoms resolve; if no further complications ensue after 30 minutes, the rate may be increased to 100% of the original infusion rate. Monitor subject closely. If symptoms recur, then no further BMS-936558 will be administered at that visit.
- For future infusions, the following prophylactic premedications are recommended: diphenhydramine 50 mg (or equivalent) and/or acetaminophen/paracetamol 325 to 1000 mg should be administered at least 30 minutes before nivolumab or ipilimumab infusions. If necessary, corticosteroids (up to 25 mg of hydrocortisone or equivalent) may be used.

For Grade 3 or 4 symptoms: (severe reaction, Grade 3: prolonged [ie, not rapidly responsive to symptomatic medication and/or brief interruption of infusion]; recurrence of symptoms following initial improvement; hospitalization indicated for other clinical sequelae (eg, renal impairment, pulmonary infiltrates). Grade 4: Life-threatening; pressor or ventilatory support indicated):

- Immediately discontinue infusion of nivolumab or ipilimumab. Begin an IV infusion of normal saline and treat the subject as follows: Recommend bronchodilators, epinephrine 0.2 to 1 mg of a 1:1000 solution for subcutaneous administration or 0.1 to 0.25 mg of a 1:10,000 solution injected slowly for IV administration, and/or diphenhydramine 50 mg IV with methylprednisolone 100 mg IV (or equivalent), as needed. Subject should be monitored until the Investigator is comfortable that the symptoms will not recur. Nivolumab or ipilimumab will be permanently discontinued. Investigators should follow their institutional guidelines for the treatment of anaphylaxis. Remain at bedside and monitor subject until recovery of the symptoms.

In case of late-occurring hypersensitivity symptoms (eg, appearance of a localized or generalized pruritus within 1 week after treatment), symptomatic treatment may be given (eg, oral antihistamine or corticosteroids).

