## **4.5 Selection and Timing of Dose for Each Subject**

### **4.5.1 Dosing**

#### **4.5.1.1 Nivolumab plus Ipilimumab Dosing (Arm A)**

Subjects randomized to Arm A will receive nivolumab at a dose of 3 mg/kg as a 30-minute IV infusion, on Day 1 of each treatment cycle every 2 weeks and ipilimumab at a dose of 1 mg/kg every 3 cycles (ie, every 6 weeks) until progression, unacceptable toxicity, withdrawal of consent, completion of 24 months of treatment, or the study ends, whichever occurs first.

Subjects should begin study treatment within 3 calendar days of randomization. See [Table 4.5.1.1-1](#) for details on the dosing schedule of nivolumab plus ipilimumab in Arm A.

Dosing calculations should be based on the body weight assessed at baseline. It is not necessary to re-calculate subsequent doses if the subject weight is within 10% of the weight used to calculate the previous dose. All doses should be rounded up or to the nearest milligram per institutional standard.

When study treatments (nivolumab and ipilimumab) are to be administered on the same day, nivolumab is to be administered first. Nivolumab infusion must be promptly followed by a flush of diluent to clear the line of nivolumab before starting the ipilimumab infusion. The second infusion will always be the ipilimumab study treatment and will start after the infusion line has been flushed, filters changed and patient has been observed to ensure no infusion reaction has occurred.

There will be no dose escalations or reductions of nivolumab and ipilimumab allowed. Subjects may be dosed with nivolumab no less than 12 days from the previous dose of nivolumab and may be dosed with ipilimumab no less than 37 days from the previous dose of ipilimumab. There are no premedications recommended.

Subjects should be carefully monitored for infusion reactions during nivolumab administration. If an acute infusion reaction is noted, subjects should be managed according to [Section 4.5.8](#).

Doses of nivolumab and/or ipilimumab may be interrupted, delayed, or discontinued depending on how well the subject tolerates the treatment. Please refer to [Section 4.5.2.1](#) (dose delays), [Section 4.5.4.1](#) (resuming treatment) and [Section 4.5.5.1](#) (dose discontinuation).

Table 4.5.1.1-1: Dose Schedule of Nivolumab and Ipilimumab in Arm A							

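### Section 4.5.8 stops nivolumab only for that visit when a Grade 2 infusion reaction recurs, yet the recurrence fits the section's own Grade 3 description, which requires permanent discontinuation

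*Protocol*

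**What the plan says.** The dosing sections for both nivolumab arms (4.5.1.1 for Arm A, 4.5.1.2 for Arm B) direct sites to Section 4.5.8 for acute reactions: "If an acute infusion reaction is noted, subjects should be managed according to" that section.

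Under Grade 2 symptoms, Section 4.5.8 says:

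- "Stop the nivolumab or ipilimumab infusion, begin an IV infusion of normal saline", and treat the subject.
- If the infusion was interrupted, "restart the infusion at 50% of the original infusion rate when symptoms resolve". The full rate may be resumed after 30 minutes without further complications.
- "If symptoms recur, then no further BMS-936558 will be administered at that visit".
- In the next bullet, still under Grade 2: "For future infusions, the following prophylactic premedications are recommended". No exception is written for a subject whose symptoms came back.

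Under Grade 3 or 4 symptoms, the same section describes Grade 3 as including "recurrence of symptoms following initial improvement". The action there is immediate and permanent discontinuation of nivolumab or ipilimumab. The opening paragraph of Section 4.5.8 asks for grading by NCI CTCAE version 4 and for every Grade 3 or 4 infusion reaction to be reported to the medical monitor within 24 hours.

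Section 4.5.5.1 lists a drug-related Grade 3 infusion reaction, however short, as a reason to discontinue permanently. Section 3.5 makes this binding. It opens "Subjects MUST discontinue investigational product (and non-investigational product at the discretion of the investigator) for any of the following reasons", and the Section 4.5.5 criteria are one of the listed reasons.

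**The concern.** A reaction that resolves, is re-challenged at half rate and then recurs is covered by the Grade 2 recurrence sentence and also by the printed Grade 3 description. The first limits the stop to one visit and leads into advice on later infusions. The second ends treatment. The sentence does not tell the investigator to re-grade the event and does not refer to the Grade 3 block or to Section 4.5.5.1.

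Two things are at stake. One is the safety of a subject who could receive another dose after meeting a mandatory stopping criterion; that dose would also be a protocol deviation. The other is reporting: an event left at Grade 2 would not trigger the 24-hour report to the medical monitor.

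There is a second defect in scope. The bullet begins with either drug, but the recurrence sentence names only BMS-936558, which is nivolumab. Read literally, it gives no instruction when the recurrence happens during ipilimumab.

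**Working it through.** The plan gives no figure to reproduce. The check is to follow one event through each relevant text.

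**The event:** a drug-related Grade 2 reaction during nivolumab or ipilimumab; infusion stopped; symptoms resolve; restart at 50% rate; symptoms recur.

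| Place in Protocol | Does it apply? | Instruction |
|---|---|---|
| 4.5.8, Grade 2, recurrence sentence | Yes, if the drug is nivolumab | No more nivolumab at that visit |
| 4.5.8, Grade 2, next bullet | Not excluded | Premedicate for later infusions |
| 4.5.8, Grade 3 description | Yes: symptoms improved, then returned | Event is Grade 3 |
| 4.5.8, Grade 3 or 4 action | Follows from the grade | Permanent discontinuation |
| 4.5.5.1 | Yes: drug-related Grade 3 infusion reaction | Permanent discontinuation |
| 3.5 | Yes, through Section 4.5.5 | Discontinuation is mandatory |

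The first two rows point to treatment that may resume. The last four point to treatment that has ended. If the drug is already permanently stopped, limiting the stop to that visit serves little purpose, so the wording itself suggests later dosing.

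**What the correct outcome would be.** It depends on drug and arm:

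- Arm A, nivolumab discontinuation criteria met: both drugs stop (Section 4.5.5.1).
- Arm A, only ipilimumab criteria met: nivolumab may continue, once the event has fully resolved and any steroids given for it have been stopped (Section 4.5.5.1).
- Arm A, causative drug cannot be determined: both stop (Section 4.5.5.1).
- Arm B, nivolumab criteria met: chemotherapy may continue, unless the investigator cannot tell which treatment caused the event, in which case everything stops (Section 4.5.5.2).

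The recurrence sentence leads to none of these rules.

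**Section 4.5.4.1.** This section replaces an ipilimumab dose that was missed because of a same-day nivolumab reaction, with the next combined dose at least 37 days later. It therefore foresees reactions that disrupt one visit without ending treatment. That is consistent with the rules above if it is applied to reactions that do not meet discontinuation criteria.

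**Size.** Randomization is 1:1:1 with about 939 subjects planned (Section 3.1), so 939 / 3 = 313 per arm and 2 × 313 = 626 in Arms A and B. The documents give no rate of recurrence after restart. Section 1.1.7 reports infusion-site and hypersensitivity reactions of 1.7%, 3.7% and 18.5% at 0.3, 2 and 10 mg/kg in another study, all Grade 1 to 2. These are not recurrence rates and cannot be used here.

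**The case against.** The strongest reply is that the safeguard is already written. The Grade 3 description and its permanent stop follow closely in the same section, CTCAE grading is required, and Sections 4.5.5.1 and 3.5 are mandatory. An investigator can apply the texts in sequence: stop at that visit, re-grade, discontinue. The recurrence sentence does not mention later visits, and the premedication bullet is about Grade 2 reactions in general. Section 4.5.8 also calls its content recommendations that may be adapted to local standards.

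Much of this stands. A reader might infer that the protocol authorizes re-dosing after a recurrence. The documents do not support that: the mandatory criteria should control, and re-dosing follows only from reading the recurrence sentence together with a bullet that lacks an exception. A reader might also infer that sites in both arms see only Section 4.5.8. For Arm A that is wrong, because the next paragraph of Section 4.5.1.1 names Section 4.5.5.1 for discontinuation. The nivolumab paragraphs of Section 4.5.1.2 for Arm B have no such pointer, though Section 3.5 covers both arms. Nor does any nivolumab reaction in Arm A end both drugs; that holds only when nivolumab discontinuation criteria are met.

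What does not stand is that the conflict is thereby resolved. The step of re-grading is not written anywhere. The local-adaptation clause covers the treatment recommendations of Section 4.5.8 and does not relax Sections 3.5 or 4.5.5.1. It therefore cannot reconcile the recurrence sentence with them.

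**Conclusion.** The inconsistency is real and should be corrected. The Grade 2 recurrence sentence conflicts with the Grade 3 description in its own section and with the permanent discontinuation required by the Grade 3 or 4 action, Section 4.5.5.1 and Section 3.5. It also omits ipilimumab.

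The practical effect is likely to be small. A wrong dose needs a recurrence after restart and then an investigator who overlooks the Grade 3 text and the mandatory criteria. The pool is about 626 planned subjects, but the number wrongly re-dosed cannot be estimated from the documents. It would be tempting to assume a recurrence rate of, say, 0.1% to 1% and quote 626 × 0.001 = 0.6 to 626 × 0.01 = 6.3 subjects. That range is an assumption without a source in the documents, and it would count recurrences; wrong re-dosing could only be a part of them.

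The conclusion rests on treating return of symptoms after resolution and restart as recurrence in the sense of the printed Grade 3 description, and on the event being drug-related. No power, alpha, event count or sample-size figure is affected.

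**What to change.** In Section 4.5.8, replace the Grade 2 recurrence sentence with:

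*If symptoms recur after restart, stop the infusion of the drug being given (nivolumab or ipilimumab), grade the event as Grade 3, report it within 24 hours, and follow the Grade 3 instructions and Section 4.5.5.1.*

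Limit the premedication bullet that follows to Grade 2 reactions without recurrence. The reference to Section 4.5.5.1 brings in the Arm A rules on which drug stops. Continuation of chemotherapy in Arm B is already covered by Section 4.5.5.2. Section 4.5.4.1 can stay as it is, because it applies to reactions that do not meet discontinuation criteria.

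If the medical team does intend to allow re-treatment after a recurrence, that exception should be stated in both Section 4.5.8 and Section 4.5.5.1.

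The cost is one replaced sentence and one limiting phrase, by administrative letter or in the next amendment. No new visit, procedure or data item is needed.
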